
Our overarching research goal is to help reduce early morbidity from aging and mortality associated with infection in the aged by developing probiotics with the potential to enhance the health benefits of *Triphala* to reverse chronic inflammation and stimulate immune robustness. Our project is based on the hypothesis as well as *in vitro* data from our laboratory which demonstrate that the bioactivity of *Triphala* is elicited by the gut microbiome to generate a widened spectrum and abundance of anti-inflammatory compounds. We reason that the *Triphala*-induced benefits to both the elderly as well as persons of all ages can be enhanced by co-administration of specific probiotic species. *Thus, we hypothesize that probiotic formulations consisting of bacterial species capable of mediating the increased digestion, bioabsorption and bioactivity of Triphala will increase and make more uniform the response and impact of Triphala treatment on human populations. We hypothesize that the potent anti-inflammatory Triphala when co-administered with VSL#3 will further reduce inflammation and promote a healthier gut community architecture in the elderly.*

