## **Assessment Outcomes**

Outcomes Hypothesis: Feasibility, treatment expectancy/satisfaction, retention, and adherence.

Recruitment rates will be recorded and new recruitment strategies will be formulated to overcome barriers presented by decliners for a future study. Treatment expectancy and satisfaction - 6 item credibility/expectancy questionnaire (CEQ) will be utilized. Retention (% of drop-outs) will be recorded, and exit interviews will be administered to determine reasons for drop-out. Adherence to intervention will be derived from T1 and T2 presence.

Outcomes Hypothesis: Objective measures of gut microbiome health.

*16S rDNA Sequencing:* Stool samples will be analyzed to identify alterations in the gut microbiota community structure by 16S rDNA sequencing. This experimental design will allow us to assess the efficacy of *Triphala* and probiotic species to positively modulate inflammaging and immunosenescence. We will also assess a panel of 30 cytokine/chemokines/lymphokines for this purpose. Finally, our study design permits us to evaluate potential synergistic interactions between the probiotic species and *Triphala*.

Outcomes Hypothesis: Objective measures of inflammatory status.

*Blood pressure (BP):* 3 resting automated BPs will be taken (Dinamap 1846SX) and averaged.

*Biomarkers:* Blood samples will be obtained by a licensed phlebotomist from a mobile phlebotomy service, Veni-Express in SOM Building 4's Clinical Rooms. Serum heparin or EDTA-preserved plasma will be stored at -80° C until assay in [name] laboratory space MTF-418. Inflammatory biomarkers will be assessed by ELISA (MSD, Minneapolis, MN).

For those participants who specifically consent to tissue banking in the ICF, their samples will remain in storage in [name] laboratory space MTF-418 after the end of this study. These blood and stool samples will remain under the sole control of the PI and may be investigated later for other inflammation-related biomarkers and gut microbes.

Exploratory Outcomes Hypothesis: Health-related behaviors.

*Pittsburgh Sleep Quality Index (PSQI):* A self-report of sleep quality and disturbances over a 1-month period.

Nineteen items generate seven "component" scores. The sum of scores yields one global score;

*Fruit/Vegetable/Fiber Screen and Fat Screen:* Rapid screeners with high correlations for total fat, saturated fat, cholesterol, fruit/vegetable intake.

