#### Additional Measures

Age, gender, socio-economic status, ethnic group, relationship status, education, body-mass Index and waist-hip circumference will be recorded. If for medical reasons subjects alter medications, it will be recorded via a monthly tracking form that the subject can submit.

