#### **Statistical Issues**

Analytic Approach. Summary statistics (means, SDs, ranges, frequencies) will be computed for all variables of interest and compared between the treatment arms at baseline using 2-sample tests to test if randomization achieved balance in key covariates across groups. In the event of pre-existing variable group differences associated with dependent or relevant clinical variables, the nuisance variables will be statistically controlled. Outcome measures (e.g. health-related behaviors, psychological health, and objective measures of microbiome health and inflammation) will be transformed as needed to better approximate Gaussian distributions. The proposed study period is 2 months; hence we anticipate little loss-to-follow-up. However, subjects may drop out for a variety of reasons. It is important to take missing data into account when testing hypotheses of interest. Mixed-models can be applied even if some observations are missing as long as the data are "missing at random". Missing data (e.g., drop-outs) will be tested to determine if it is informative, and the methods to test for completely random dropouts will be applied. If needed, pattern-mixture models will be developed which take "missingness" into account when estimating parameters of interest using the methods of Park & Lee.

Analysis Plan. Two sample *t*-tests will be used to compare change scores (post-treatment minus pretreatment) in each outcome. Given the multiple outcomes, we will also use O'Brien's test which can be used to compare multiple endpoints across groups; we will apply O'Brien's test to the multiple outcomes for each hypothesis (e.g., psychological health via positive and negative affect, depressive symptoms; health behaviors via diet, physical activity, medication adherence, and alcohol usage). The O'Brien test statistic is a weighted linear combination of the *t*-statistics for each outcome. Finally, we will fit mixed effects models, with a subject-specific intercept included to allow for individual variability in outcome. Main covariate effects will be treatment group, time (pre-treatment and immediately post-treatment), and the group X time interaction. Likelihood ratio tests will be used to test the significance of these covariates. A significant group X time interaction will indicate that outcome trajectories differ across treatment groups.

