Sample Size and Power. We hypothesized a Cohen's *d* effect-size (standardized mean difference between groups) of 0.75 based on previous studies. With at least 60 subjects completing 2 visits, we will have 80% power (2-sided alpha=0.05) to detect a 0.75 effect-size (Cohen's *d*). To be conservative, we aim to recruit 75 subjects to this study, allowing for a 20% drop-out/loss-to-follow-up rate and a total of 60 subjects completing the 2 visits. Note that our calculations did not control the Type I error for the multiple endpoints. Our objective in this small pilot study is to obtain early evidence of the putative efficacy of this novel intervention on a multitude of outcomes, psychosocial and biological, in the elderly. We expect our findings to inform the design of a larger future clinical trial in elderly subjects.

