### **14. POTENTIAL RISKS**

Participation in this study may involve some added risks or discomforts. These include:

- a. Pain, risk of fainting, lightheadedness and dizziness associated with the blood draw.
- c. Mild soreness and/or a bruise at the needle site.
- d. A small risk also exists that the vein may form a clot at the needle stick, which will gradually clear over one to two weeks.
- e. Risk of local infection at blood draw site.
- f. There is risk of loss of confidentiality. This will be minimized by using an identifier number rather than patient's name on all of the information gathered for the study.
- g. There may be mild psychological discomfort answering personal questions.
- h. There may be mild psychological discomfort providing a stool sample.
- i. There is an additional risk of bleeding for people taking blood thinning medications. Though considered to be a low risk, participants may want to discuss this with their physician prior to enrolling in the study.

Since this is an experimental treatment, there may be some unknown risks that are currently unforeseeable.

There are no known drug interactions or medical risks known with taking *Triphala*; a side effect of *Triphala* includes potential slightly looser bowel movement that is transient or resolves upon reduction of dose or cessation of *Triphala*. VSL#3 may cause a side effect of possible mild abdominal bloating in the first few days of consumption, which is a transitory phenomenon due to changing intestinal microflora that is self-resolving or can be reduced by decreasing the daily probiotic dose.

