## **18. RISK/BENEFIT RATIO**

Both the risks and the benefits to individual participants are relatively low. There are no known drug interactions or medical risks known with taking *Triphala*; a side effect of *Triphala* includes potential slightly looser bowel movement that is transient or resolves upon reduction of dose or cessation of *Triphala*. VSL#3 can cause a side effect of possible mild abdominal bloating in the first few days of consumption, which is a transitory phenomenon due to changing intestinal microflora that is self-resolving or can be reduced by decreasing the daily probiotic dose.

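### Adherence is scored from attendance at T1 and T2, so it repeats retention and counts every T2 attender as adherent whatever they took

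*Combined protocol and SAP*

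**What the plan says.** Assessment Outcomes in Section 9 groups feasibility, treatment expectancy and satisfaction, retention, and adherence as outcomes. Two sentences define the last two:

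- Retention: "Retention (% of drop-outs) will be recorded, and exit interviews will be administered to determine reasons for drop-out".
- Adherence: "Adherence to intervention will be derived from T1 and T2 presence".

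The Treatments and Experimental Conditions text has product supplied at T1 and taken at home, morning and night. The synbiotic and herb-only regimens differ only by one VSL#3 capsule at each dosing time.

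Sections 14 and 18 acknowledge that intake may fall. Triphala may cause "slightly looser bowel movement that is transient or resolves upon reduction of dose or cessation of" the herb. Bloating on VSL#3 is described as mild and self-resolving, or as something that "can be reduced by decreasing the daily probiotic dose".

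**The concern.** Two outcomes with different names come from one fact, whether the participant attended. The adherence outcome therefore carries no information beyond retention, and it cannot register a participant who attends T2 after skipping, reducing or stopping product.

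Two uses of the pilot are at stake. The first is feasibility, where adherence is a listed outcome and would be reported with a value that does not describe supplement use. The second is interpretation of the synbiotic-versus-herb contrast. Section 7 hypothesises that suitable probiotics "will increase and make more uniform the response and impact of Triphala treatment on human populations". If that contrast is weak, null or uneven, an obvious question is whether the capsules were taken, and the plan collects nothing described as answering it.

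**Working it through.** **Inputs.** 75 recruited, 20% drop-out and 60 completing both visits (Statistical Issues, Sample Size and Power); 20 per group in 3 groups (Section 10); 8 weeks of supplementation (Section 5); two dosing times a day (Experimental Conditions).

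**1. Reproduce the plan's own figure.** Completers = recruited x (1 - drop-out) = 75 x (1 - 0.20) = 60, and 60/0.80 = 75. The stated figures agree.

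**2. Apply the adherence rule.** Anyone who has product was at T1, because that is where it is supplied. Presence at both visits therefore reduces to presence at T2.

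- All recruited: 60/75 = 0.80 = 1 - 0.20, the complement of drop-out.
- Those with T2 data: 60/60 = 1.00, by definition.

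**3. Compare with what could have been taken.** Scheduled dosing times per person are 8 x 7 x 2 = 112. Let d be the number taken, up to 112.

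- Attender at T2: true share d/112, recorded value 1, error 1 - d/112, which is zero or positive. With d = 0 the error is 1. Someone who took one VSL#3 capsule a day instead of two would have 56/112 = 50% for that product and be recorded as adherent.
- Person who misses T2: recorded as not adherent, true share d/112, so the record is right or too low.

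Among attenders the direction of error is fixed: right or too high. Over all 75 it is not, because the two errors run in opposite directions.

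**4. Look for an intake record elsewhere.**

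- Exit interviews (Assessment Outcomes) concern reasons for drop-out, so they do not reach attenders who stopped product.
- Additional Measures: "If for medical reasons subjects alter medications, it will be recorded via a monthly tracking form that the subject can submit". This covers medication changes, is not described as covering study product, and is submitted at the participant's option.
- Data Safety Monitoring Plan (Section 15): health status is reported monthly and adverse events are reviewed. Doses are not mentioned.
- Analysis Plan: adherence appears once more, among "health behaviors via diet, physical activity, medication adherence, and alcohol usage", but no section describes a measure of study-product intake that would feed it.
- T2 stool: the microbiome is the primary outcome, and Section 7 says compounds in Triphala themselves promote Lactobacillus and Bifidobacteria. Their abundance cannot double as an intake check.

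No capsule count, diary, returned-product check or dose question is described.

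**5. Consequence for the contrast.** A synbiotic participant who took all the Triphala and no VSL#3 would have the same intake as the herb-only arm, yet would be scored adherent to the synbiotic. This shows what the rule cannot detect. It does not predict how often it happens.

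**The case against.** The strongest case on the other side is about weight. Adherence is not among the aims in Section 6. The analysis sets no adherence threshold, no per-protocol population and no progression rule. The side effects are described as mild and transient, and Sections 14 and 18 are risk disclosures that instruct nobody to cut the dose; for VSL#3 they mention a lower dose only, not stopping. People who cut back because of side effects might also surface in the monthly health-status reports. Any count is imperfect too: capsules get discarded, self-report errs, and those who miss T2 have no count.

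Most of this stands, and it limits the point to a feasibility outcome and to interpretation. It does not rescue the definition, because a health report is not a dose record and an imperfect intake measure still tells more than a second copy of retention.

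Stronger readings that a reader might infer, and that the documents do not support:

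- *That the between-arm results are biased or invalid.* Comparing arms as assigned does not use the adherence variable, and its estimates do not change.
- *That many participants will stop, or that power falls by a known amount.* The documents give no rate of stopping or reduction, so no such figure can be derived.
- *That the plan commits to carrying this adherence figure into the next trial.* Statistical Issues says "We expect our findings to inform the design of a larger future clinical trial in elderly subjects" but does not mention adherence there. The link rests only on adherence being listed with feasibility in Assessment Outcomes.

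**Conclusion.** The point holds in a limited form. A named outcome is defined by a stated rule that cannot measure it: at planned completion it returns 80% overall and 100% among T2 attenders, whether those attenders took 0 or 112 of their scheduled doses. The adherence figure among attenders can be right or too high, never too low, assuming nobody takes more than assigned. Non-intake cannot be examined as an explanation for a weak or null synbiotic-versus-herb difference.

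The actual size of the overstatement is unknown. It could be small, given the mild side effects described. The conclusion assumes that no intake record exists outside the visible text. It should be corrected before the trial reports feasibility, but it does not threaten the planned comparisons.

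**What to change.** In Assessment Outcomes:

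- Report presence at T1 and T2 as retention (visit completion) only.
- Define adherence as the share of assigned capsules taken = (capsules dispensed at T1 - capsules returned at T2) / capsules assigned over 8 weeks. Partial doses then count in proportion.
- Count Triphala and VSL#3 separately in the synbiotic arm, and report adherence by arm.
- Use a short self-report question at T2 when product is not returned. The count takes precedence when it is available.

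To make this workable:

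- Record the number of capsules dispensed at T1, and state how many Triphala capsules make up 2 g, which the protocol does not give. The VSL#3 denominator is 112 capsules; placebo, at two per dosing time, is 2 x 112 = 224.
- Have unblinded staff do the count after the T2 measures, because the kits differ by arm and assessors are to stay blind. The Project Coordinator is a natural choice, being already the person asked to break the code under Section 15.
- Add an item to the monthly form in Additional Measures for study product stopped or reduced, with date and reason.

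**Cost.** No extra visit is needed. At an assumed 5 minutes each, 60 participants need 60 x 5 = 300 minutes, or about 5 staff hours, plus one form item. The remaining weaknesses are capsules discarded and so counted as taken, self-report error, and no count for those who miss T2.

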## 9. RESEARCH DESIGN AND METHODS

**Recruitment.** A total of 75 participants will be recruited from UCSD ADRC. We aim to recruit approximately 20 eligible individuals per group (1. synbiotic, 2. herb alone, and 3. placebo control) from UCSD ADRC.

**Screening.** After written consent, patients will undergo a medical history intake to determine eligibility. Along with study participants' referring providers, ADRC will provide oversight in determining whether potential subjects are eligible according to the following criteria:

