**11. RECRUITMENT AND PROCEDURES PREPARATORY TO RESEARCH**

**Overview.** A total of 75 participants who are generally healthy and otherwise meet our study criteria will be recruited and randomly assigned to either an 8-week synbiotic group, herb alone, or placebo control with a goal to obtain 60 patients who complete the study (20 in each group) after an estimated 20% attrition. Placebo control subjects will be given the option of having the 8-weeks of herbal synbiotic for directed personal use upon conclusion of the study. [name] has volunteered to help identify individuals who meet criteria for this study. Additional staff members responsible for assisting with recruitment are listed elsewhere in this application.

With this application, we are requesting a Waiver of Documented Consent to conduct the telephone screens. Asking interested individuals whether they meet the basic study criteria over the telephone (age, immune disorder diagnosis, medication use) presents no more than minimal risk of harm and involves no procedures for which written consent is normally required outside of the research context. Written consent will be obtained at the initial, in-person visit before any study questionnaires are administered or research procedures are performed.

With this application, we are also requesting a partial waiver of HIPAA authorization so that our study staff may help clinical staff identify potentially eligible participants using EPIC. When a member of our research team identifies a patient who may be eligible, he or she will then send a secure EPIC email asking the provider if they agree that a given patient is a good candidate for the study and asking the provider to speak with his or her patient about our study. The provider will provide a brief overview of the study during the patient's clinical

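### The three-arm design cannot evaluate synergy between VSL#3 and Triphala, because VSL#3 is never given alone

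*Combined protocol and SAP*

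**What the plan says.** In section 9, Assessment Outcomes, the paragraph on 16S sequencing ends by saying that "our study design permits us to evaluate potential synergistic interactions between the probiotic species and" *Triphala*. Earlier in the same paragraph, the design is said to allow assessment of the efficacy of *Triphala* "and probiotic species to positively modulate inflammaging and immunosenescence".

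Section 7 reasons that the benefits of *Triphala* "can be enhanced by co-administration of specific probiotic species". It then states the hypothesis that suitable probiotic formulations "will increase and make more uniform the response and impact of Triphala treatment on human populations".

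The arms are the same throughout. Section 9, Recruitment, lists them as "1. synbiotic, 2. herb alone, and 3. placebo control", and in section 11 participants are "randomly assigned to either an 8-week synbiotic group, herb alone, or placebo control". Under Experimental Conditions, VSL#3 appears only in the synbiotic kit, together with *Triphala*.

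The Analysis Plan under Statistical Issues uses two-sample t-tests on change scores, O'Brien's test, and a mixed model with group, time and their interaction. Of that interaction it says: "A significant group X time interaction will indicate that outcome trajectories differ across treatment groups".

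**The concern.** Synergy means that the combination does more than the sum of its parts. To judge that, each part must be observed alone, and VSL#3 is not. A synbiotic arm that does better than the herb arm is what one would see if VSL#3 simply had its own effect and *Triphala* played no part in it.

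The documents make that explanation plausible. Section 5 names VSL#3 among probiotics linked to gut microbial and anti-inflammatory benefit. Section 7 says that the two genera it contains reduce inflammation in humans. Section 9 describes it as already prescribed for its effect on gut flora, and the stool microbiome is the primary outcome.

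The risk is that a synbiotic versus herb difference is reported as synergy, or as potentiation of *Triphala*, when VSL#3 alone could account for it. The Sample Size and Power text says that the findings are meant to inform a larger trial, so the misreading could carry forward.

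**Working it through.** **Inputs.** Three arms (section 9, Recruitment and Experimental Conditions; section 11). Effect size d = 0.75, two-sided alpha 0.05, 60 completers, 20% drop-out (Sample Size and Power). 20 completers per group (section 10). The documents give no effect for VSL#3 alone.

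**The plan's own figure.** The protocol states that "we will have 80% power (2-sided alpha=0.05) to detect a 0.75 effect-size". For a pairwise comparison of 20 versus 20, power is 0.66 by the normal approximation and 0.64 by the t distribution, so the 80% is not reproduced for that contrast. The recruitment figure is reproduced: 60 / (1 − 0.20) = 75. The power shortfall is a separate matter. Here 0.75 serves only as a scale for illustration.

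**Step 1: arm means.** Let m be the mean change on placebo, T the effect of *Triphala* alone, V the effect of VSL#3 alone, and TxV the interaction (synergy if it adds to the benefit).

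| Arm | Mean change |
|---|---|
| Placebo | m |
| *Triphala* alone | m + T |
| Synbiotic | m + T + V + TxV |

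**Step 2: what the contrasts estimate.**

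- Herb − placebo = T.
- Synbiotic − herb = V + TxV.
- Synbiotic − placebo = T + V + TxV.

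**Step 3: estimability.** With columns (m, T, V, TxV), the design matrix has rows [1,0,0,0], [1,1,0,0] and [1,1,1,1]. Its rank is 3 for 4 parameters. A contrast is estimable only if adding it as a row leaves the rank at 3.

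| Contrast | Rank after adding | Estimable |
|---|---|---|
| T | 3 | yes |
| V + TxV | 3 | yes |
| T + V + TxV | 3 | yes |
| V | 4 | no |
| TxV | 4 | no |

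Moving any amount from V to TxV leaves all three arm means unchanged. Sample size does not enter.

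**Step 4: the planned analyses.** With three arms and two times, group-by-time has (3 − 1) × (2 − 1) = 2 degrees of freedom. Its null hypothesis is T = 0 and V + TxV = 0, so it contains no separate *Triphala*-by-VSL#3 term. The t-tests compare arm means, and O'Brien's statistic combines those t-statistics, so both carry the same limit.

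**Step 5: size, by illustration.** Suppose synbiotic − herb = 0.75 SD. Then TxV = 0.75 − V. V is assumed over 0 to 1.00 SD.

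| Assumed V (SD) | Implied TxV (SD) | Reading |
|---|---|---|
| 0 | +0.75 | all synergy |
| 0.25 | +0.50 | part synergy |
| 0.50 | +0.25 | part synergy |
| 0.75 | 0 | purely additive |
| 1.00 | −0.25 | antagonism |

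The same trial data fit every row.

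**Step 6: what a VSL#3-alone arm would do.** Adding the row [1,0,1,0] brings the rank to 4, and TxV becomes estimable. The interaction contrast has variance 4 × SD² / n per arm. At n = 20 the standard error is √(4/20) = 0.447 SD, so a 0.75 SD interaction (assumed equal to the protocol's d) gives 0.75 / 0.447 = 1.68 and power of about 0.38 (t distribution). With 60 completers split 4 × 15, power is about 0.30. For 80% power, n per arm = 4 × ((1.96 + 0.84) / 0.75)² ≈ 56, or 57 by the t distribution. That is 224 to 228 completers, or 280 to 285 recruited at 20% drop-out.

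**The case against.** The strongest reply is that this is one closing sentence in an outcomes paragraph of a small pilot. Synergy is not an aim in section 6, no test of it is planned, and nothing is powered on it. The sentence speaks only of evaluating potential interactions. If VSL#3 alone is taken not to be harmful (V ≥ 0), the synbiotic versus herb difference is an upper limit on synergy, so some evaluation is possible. Section 7 is background, and greater uniformity of response can be compared between the two arms. The efficacy phrase can also be read as meaning the combination.

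Some of this stands. The aims are untouched. So is the section 7 prediction that adding VSL#3 lowers inflammation beyond *Triphala* alone, which is testable as an added effect. Spread of response can be compared, although a difference could not be attributed to better use of *Triphala* rather than to VSL#3 itself. The efficacy phrase is a problem only if it means separate probiotic efficacy.

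The rest does not rescue the sentence. The V ≥ 0 assumption is stated nowhere, and it has no clear meaning for 16S community structure, where no scalar endpoint or beneficial direction is defined. Even where it applies, an upper limit can count against synergy but cannot confirm it. Section 7 presents potentiation as a hypothesis, not only as rationale. Pilot status excuses low power, but not a claim that no sample size could support.

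One further caution is fair. The herb-only kit lists no dummy for the VSL#3 capsule, and only assessment personnel are described as unaware of assignment. The added effect may therefore include expectancy, especially on questionnaires.

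**Conclusion.** The concern holds. The protocol claims a property that its design does not have. Neither the synergy term nor VSL#3's own effect can be estimated from these three arms, whatever the sample size; only their sum can. This conclusion rests on the arm structure alone and needs no numerical assumption. The 0.75 SD illustration does depend on an assumed range for V, and it shows that one observed difference is compatible with full synergy, none, or antagonism. The defect limits what may be concluded from synbiotic versus herb. It does not impair the stated aims or the planned comparisons.

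**What to change.** In section 9, Assessment Outcomes, replace the synergy sentence with:

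> The design estimates the added effect of giving VSL#3 with *Triphala* (synbiotic versus herb alone) and the effect of *Triphala* (herb alone versus placebo). It cannot distinguish synergy from an additive VSL#3 effect, because VSL#3 alone is not studied.

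Under Statistical Issues, state that a synbiotic versus herb difference will be reported as an added effect and not as evidence of synergy or potentiation.

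Align the two related statements. In section 7, keep potentiation as the rationale and say that it is tested here only as an added effect. In the 16S paragraph, refer to the efficacy of *Triphala* and of *Triphala* plus VSL#3.

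The cost is a few sentences and the loss of any synergy or potentiation conclusion. Arms, endpoints, tests and sample size stay as they are. If the sponsor wants to keep the synergy question, it needs a VSL#3-alone arm and an interaction contrast. At 20 completers per arm that would have only about 38% power for a 0.75 SD interaction, so the question fits the larger trial better.
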